13.2 Reporting of Adverse Events

Any AEs that occur after a patient has signed the Informed Consent Form and up to 12 weeks after Day 0, must be reported, whether or not it is considered related to any of the study medications.

After 12 weeks post last administration of study treatment, only new onset AESIs, and study treatment-related AEs and SAEs must be reported when they come to the investigator's attention.

All AEs will be reported in the patient eCRFs. If more than one AE occurs, each event should be recorded separately. AEs and/or laboratory abnormalities shall be reported to the Sponsor

according to the reporting requirements and within the time periods specified in the protocol. All AEs will be followed up until resolved or as clinically required.

Specific information about secondary malignancies such as leukaemia, MDS and aplastic anaemia or any other malignancy, will be collected up to 5 years after study medication administration or relapse of disease, including information about treatment given to the patient due to NHL. See also paragraph on Adverse Events of Special Interest in [Section 13.1.7](#).

Death is not defined as an AE but as an outcome of an AE. It is important that the event leading to the death is reported. If death is the outcome of an AE, it will be reported as such for (i) all AEs regardless of relationship to study treatment up to 12 weeks after the last administration of study treatment and (ii) AESI, and study treatment related AEs and SAEs with onset >12 weeks after the last administration of study treatment.

Progression of disease:

- **Part A:** Progression of disease will be reported as an AE until Week 12. Thereafter progression of disease will be recorded in the eCRF and still used as an efficacy endpoint. It will be the SRC who will decide if a fatal outcome of disease progression should be considered as an expected AE. This will depend on the information received and medical consideration.
- **Part B and C:** Disease progression is not reported as an AE if it is clearly consistent with the suspected progression as determined by the protocol. Hospitalisation due solely to disease progression should NOT be reported as a SAE. Any associated symptoms may be reported as adverse events if there is any uncertainty about the symptom being exclusively due to disease progression, or if it does not fit the expected pattern of progression of the disease.

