13.3 Reporting of Serious Adverse Events

13.3.1 Investigator's Responsibilities

The investigator shall report all SAEs, regardless of suspected causality, immediately (within

24 hours of the investigator becoming aware of the event) to the Sponsor or assigned designee. The immediate report shall be followed by detailed written report(s).

SAEs will be reported in the following time periods:

- SAEs will be collected from signing informed consent to ensure that any protocol-related SAEs are collected.
- Up to 12 weeks after the last administration of study treatment, whether or not considered related to IMP.
- At any time after 12 weeks after the last administration of study treatment when it comes to the investigator's attention and is judged to be related to the patient's participation in the study or related to IMP.

Any SAEs experienced after this 12 week period should only be reported to the Sponsor or assigned designee if the investigator suspects a causal relationship to the study treatment, or if it is an AESI (see [Section 13.1.7](#)). Recurrent episodes, complications or progression of the initial SAE must be reported as follow-up to the original episode within 24 hours of the investigator receiving the follow-up information. An SAE occurring at a different time interval or otherwise considered completely unrelated to a previously reported one should be reported separately as a new event.

All SAEs must be reported to Sponsor or assigned designee as follows:

1. Immediately (within 24 hours of discovery of the event) report the event by email, telephone or fax.
2. Complete the SAE report form and send within 3 working days of the discovery of the event.
3. Follow-up the SAE until resolved or as clinically required, all follow-up evaluations must be reported.
4. Record the SAE in the patient eCRFs provided.
5. Document the SAE in the hospital records.

It is important to send "as complete as possible" a report within the timelines. Incomplete information must NOT delay reporting of SAEs. Additional information must be reported once it is available; in follow-up reports using the same SAE forms, but marked as a follow-up report. In Part A, SAEs/SUSARs will be reviewed by both the SRC and the Sponsor.

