2.1.1 Visit Structure

The visit structure and the schedule of assessments are detailed in Tables 6-7, 6-8 and 6-9 in the study protocol (Section 6).

In the protocol, the Betalutin administration day is referred to as Day 0. However, for statistical analysis and to be in line with CDISC (Clinical Data Interchange Standards Consortium) requirement, the Betalutin administration day will be defined as study Day 1. See Section 3.3 for more details.

The study treatment period starts with the single dose infusion of rituximab (375mg/m²) 14 days prior to the administration of Betalutin and lasts for 12 weeks after the Betalutin administration for each participant.

The follow-up period starts from 12 weeks (3 months or 92 days) after the first lilotomab/Betalutin administration up to 5 years as follows (see Protocol Section 6.3 Schedule of Assessments for more details):

- Extensive follow-up (hospital visits): for all participants, every 3 months after Betalutin administration for the first year (i.e. Month 3, Month 6, Month 9, and Month 12). In addition, there will be an additional hospital visit at Week 4 and Month 2 after Betalutin administration. Tumour imaging assessments are only required until the participant has disease progression as confirmed by the IRC or further anticancer therapy prior to progression. All other scheduled assessments are performed regardless of disease progression or administration of further therapy.
- After Month 12: follow-up will continue every 6 months up to 5 years after the Betalutin dose.
 - Extensive follow-up (hospital visits) will be performed until the participant has disease progression as assessed by the IRC or further anticancer therapy prior to progression.
 - Survival Follow-up: Thereafter, the participant will continue limited follow up every 6 months for potential long-term toxicity (new onset of Adverse Events of Special Interest (AESIs), Adverse Drug Reactions (ADRs) and study treatment-related Serious Adverse Events (SAEs), Overall Survival, further anticancer treatment and immunogenicity assessment (ADA, if applicable). Unless blood sampling is required for immunogenicity, limited follow-up visits can be performed by telephone.

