3.5.2 Participant Disposition

A summary of participant disposition will be provided. This summary will present number of participants applicable to each of the following:

- Screened set, including screen-failures with reason.
- SAF.
- Efficacy Analysis Set.
- Gave consent for genomic biomarker analysis of tumour tissue (listing only).
- Gave consent to HLA typing (listing only).
- Gave consent for taking part in PK assessments (listing only).
- Gave consent for taking part in dosimetry assessments (listing only).
- Participants who completed the treatment period. (was in study up to Day 92).
- Participants who discontinued during the study treatment period (up to Day 92) (with summary of reasons for withdrawal from the Completion / Withdrawal eCRF page).
- Participants who discontinued after the study treatment period (from Day 93 onwards) (with summary of reasons for withdrawal from the Completion / Withdrawal eCRF page).

The treatment period is from Day 1 to Day 92 inclusive.

All duration derivations (months) are calculated relative to the date of first Betalutin administration using the following formula:

$$\text{Time to data cut off/death/withdrawal (months)} = ([\text{date of data cut off/death/withdrawal} - \text{date of first Betalutin administration}] + 1) * 12 / 365.25$$

For all summaries except the screened summary, the denominator for the percentages of participants in each category will be the number of participants in the SAF. The denominator for the percentages of participants for the screened summaries will be the number in the screened set.

Descriptive statistics for the duration of follow-up (months) will also be included where:

$$\text{Duration of follow-up (months)} = ([\{\text{latest date participant is known to be alive}\} - \text{date of first Betalutin administration}] + 1) * 12 / 365.25 \text{ rounded to 1 decimal place.}$$

Where latest date known to be alive is obtained using all data available for the participant (i.e. eCRF (including unscheduled), response and survival follow-up data).

Completion and withdrawal data, membership of each of the analysis sets along with reasons for exclusion will be listed.

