3.8.1.1 Treatment-Emergent Adverse Events

The focus of AE summarisation will be on treatment-emergent adverse events (TEAE).

Treatment-emergent adverse events AEs (TEAEs) are defined as those adverse events (AEs) occurring after first administration of rituximab or starting prior to the first administration and worsening during treatment. Adverse events with unknown onset date/time will be considered to be treatment-emergent unless the stop date/time is known to be before first administration of rituximab.

A treatment related TEAE is defined as a TEAE that is possibly or probably or definitively/certainly related to the study treatment (Betalutin, rituximab or lilotomab). If the TEAE has a missing relationship it is assumed to be related to the study treatment for analysis

purposes. This will also be derived separately for Betalutin, rituximab and lilotomab. If the TEAE has a missing relationship it is assumed to be related to all applicable study treatments for analysis purposes.

AEs will be classed as occurring in one of five periods:

- Pre-treatment - any AE that starts after the participant has provided written informed consent and that resolves prior to the first administration of rituximab, or an AE that starts prior to the first administration of rituximab and does not increase in severity after the first administration of rituximab.
- Baseline Period: any AE that starts after the participant has the first administration of rituximab but prior to the first administration of lilotomab or Betalutin (study Day 1).
- Lilotomab/Betalutin Exposure Period: any AE that occurs after the first administration of lilotomab or Betalutin (study Day 1) and upto, and including Day 92, or that is present prior to the first administration of lilotomab or Betalutin and worsens after the first administration of lilotomab or Betalutin.
- Rituximab Exposure Period: relates to the combined Baseline Period and Lilotomab/Betalutin Exposure Period (i.e. all AEs that start after the first administration of rituximab).
- Post Betalutin follow-up period: any AE which starts more than 92 days after the start of Betalutin.

All pre-treatment AEs will be excluded from the tabulations but will be fully listed.

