3.8.1.3 Lilotomab/Betalutin Exposure Period Adverse Events

The following tables will present the number of events and the number and percentage of participants experiencing TEAEs by SOC and PT for the following break points with separate summaries being produced for each:

- TEAE onset from Day 1 onwards
- TEAE onset from Day 1 to Day 92 (Month 3)

Each table will contain an overall summary. SOC and PT will be presented in descending frequency of the total number of participants with TEAEs. If a participant experiences more than one TEAE, the participant will be counted once for each SOC and once for each PT.

Table 6: LYMRIT-37-01 study, Part B and C Adverse Event Summary Tables

Summary Table	AE onset from Day 1 onwards	AE onset from Day 1 to Day 92 (Month 3)
TEAEs by SOC and PT	X	X
Serious TEAEs	X	X
Study drug related TEAEs (Betalutin, rituximab or lilotomab)		X
Serious study drug related TEAEs (Betalutin, rituximab or lilotomab)		X
TEAEs by CTCAE grading		X
most frequent TEAEs (reported in at least 5% of participants)		X

Adverse event data will be listed in full and will also include a treatment emergent flag (will distinguish pre-treatment, baseline, post treatment (day 93+), an AESI flag, the time of onset and cessation of event relative to first administration of each of rituximab, Lilotomab and Betalutin and duration of AE. Where CTCAE grade changes over time, the worst/most severe will be reported in summary tables.

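### SAP Table 6: the two open-ended TEAE tables mix all-cause events with a later period in which only AESIs and treatment-related events are collected, without saying so

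*SAP*

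**What the plan says.** **Collection rule (protocol).** Section 13.2 sets the all-cause period: "Any AEs that occur after a patient has signed the Informed Consent Form and up to 12 weeks after Day 0, must be reported". It then narrows: "After 12 weeks post last administration of study treatment, only new onset AESIs, and study treatment-related AEs and SAEs must be reported". Section 13.3.1 applies the same limit to serious events, with AESIs as the other exception: "Any SAEs experienced after this 12 week period should only be reported to the Sponsor or assigned designee if the investigator suspects a causal relationship". Table 6-8 (Parts B and C) agrees. The general AE and SAE rows are marked up to Month 3. From Month 6 only the rows for adverse drug reactions, treatment-related SAEs and AESIs remain.

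**Tables (SAP).** Section 3.8.1.3 plans summaries for "TEAE onset from Day 1 onwards" and for onset from Day 1 to Day 92. Table 6 marks the open-ended column for two table types: TEAEs by SOC and PT, and serious TEAEs. It marks the Day 1-92 column for all six types. The related and serious related tables therefore stop at Day 92.

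**Periods (SAP).** Section 2.1.1 states: "The follow-up period starts from 12 weeks (3 months or 92 days) after the first lilotomab/Betalutin administration up to 5 years". Section 3.5.2 states: "The treatment period is from Day 1 to Day 92 inclusive". Section 3.8.1.1 defines "Post Betalutin follow-up period: any AE which starts more than 92 days after the start of Betalutin", but no row or column of Table 6 uses that period.

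SAP 2.1.1 does mention that limited follow-up beyond Month 12 covers AESIs, adverse drug reactions and related SAEs. Nothing in section 3.8 carries this into the tables or says that collection narrows at 12 weeks.

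**The concern.** A table titled as all TEAEs, with percentages taken over the whole analysis set (SAP 3.1), will be read as all-cause incidence over follow-up. It is not. An unrelated event in month 2 enters the table; the same event in month 5 need not be reported and would normally be absent. For anyone followed past Month 3, the percentage falls short of all-cause incidence over follow-up. It also exceeds related incidence, because it contains unrelated events from the first 12 weeks. Serious TEAEs have the same problem.

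Table 6 is also the wrong way round. Related events are collected throughout follow-up but are tabulated only to Day 92. All-cause events are not collected after 12 weeks, yet their tables have no end.

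Two uses of the data are affected. The first is the comparison of regimens. Randomisation to 100/20 stopped after the interim analysis while 40/15 kept enrolling, and close-out needs only 3 months after the last 40/15 dose (SAP section 1). The last 40/15 patients therefore have less potential follow-up than the 100/20 patients. The second is late toxicity. Protocol 13.1.7 names secondary malignancy, MDS and acute leukaemia as the long-term risk, and this SAP summarises such events only inside the mixed tables.

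**Working it through.** **1. The plan's own figure.** SAP 2.1.1 equates 12 weeks, 3 months and 92 days. With the Betalutin day as Day 1 (SAP 3.3):

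- 12 weeks: 12 × 7 = 84 days after dosing, which is Day 84 + 1 = 85.
- 3 months: 3 × 365.25/12 = 91.3 days after dosing, which is about Day 92.
- Month 3 visit, Week 12 ± 7 days (protocol Table 6-8): 84 − 7 = 77 to 84 + 7 = 91 days after dosing, which is Days 78 to 92.

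So 92 days is not 12 weeks, but Day 92 is the last permitted day of the Month 3 visit.

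**2. What each Table 6 column covers**

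| Period | Collected (protocol) | Tabulated (SAP Table 6) |
|---|---|---|
| Day 1 to Week 12/Month 3 visit | All AEs and SAEs | All six types, Day 1-92 |
| Afterwards | AESIs and related events only | All TEAEs and serious TEAEs, inside the open-ended column only |
| Afterwards, as a period of its own | As above | No table |

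**3. Share of a patient's time under the restricted rule.** For m months of follow-up, D = m × 365.25/12 days and the share is (D − 84)/D. The right-hand column uses 91 days, which gives every patient the full visit window.

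| Follow-up | D (days) | (D − 84)/D | (D − 91)/D |
|---|---|---|---|
| 6 months | 182.6 | 98.6/182.6 = 54% | 91.6/182.6 = 50% |
| 12 months | 365.25 | 281.25/365.25 = 77% | 274.25/365.25 = 75% |
| 60 months (planned maximum) | 1826.25 | 1742.25/1826.25 = 95% | 1735.25/1826.25 = 95% |

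The choice between Day 85 and Day 92 hardly changes the result. The absence of an upper limit is what matters.

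**4. Boundary check.** Day 93 is 92 days after dosing. More than 92 days after dosing therefore begins at Day 94. The exposure period ends on Day 92 (3.8.1.1), so Day 93 belongs to neither. Sections 3.5.2 and 3.8.1.3 both start the later period at Day 93.

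**The case against.** The strongest reply is that the clean summaries already exist. All six table types have a Day 1-92 version, and the open-ended tables follow the protocol's TEAE definition (13.1.6), which has no end date. This is an abbreviated, descriptive SAP after early termination, with no safety hypothesis. All of that is true and limits the point to two tables. It does not make those two tables interpretable, because their titles and denominators hide the change in collection.

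A reader might also infer more than the documents support:

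- *That equating 12 weeks with 92 days causes the mixing.* It does not. An open-ended table crosses the change in collection wherever the cut is placed.
- *That Days 86-92 (7 of 92 days, 7.6%) are all under the restricted rule, so the cut should move to Day 85.* Protocol 13.2 read alone suggests this. But the Month 3 visit may fall as late as Day 92, and protocol 9.6.2.4 has it record every AE and SAE since the previous visit. A fixed Day 85 cut could drop valid all-cause events. What stands is that patients seen earlier in the window may lack all-cause data for up to those last 7 days.
- *That late events are never shown.* SAP 3.8.1.3 requires a full listing that marks onset from Day 93 and flags AESIs; deaths are listed with cause (3.8.2); raw AESI and SAE datasets are supplied (SAP Table 2). What is missing is a summary table.
- *That 95% of the open-ended tables is affected.* This is calendar time at the 5-year planned maximum, not a share of events, and the study was terminated in July 2022.
- *That the Day 92 cut in 3.5.2 misclassifies patients who finish Week 12.* This would need a patient to leave the whole study between Day 86 and Day 91. The documents show no such case.

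**Conclusion.** The point holds for the two open-ended tables. Their percentages are neither all-cause nor related incidences, and they depend on a length of follow-up that differs between patients and, potentially, between regimens. The related tables stop where they could continue, and the post-Betalutin period is defined but never summarised.

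The size depends on follow-up, which the documents do not give beyond a 3-month minimum after the last 40/15 dose. If a patient is followed for 6, 12 or 60 months, about 54%, 77% or 95% of that time is under the restricted rule. These figures assume sites report after 12 weeks only what the protocol requires. The number of events affected cannot be derived from the documents, and nothing in them shows that a safety signal is hidden.

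The 92-day wording and the unassigned Day 93 are separate, small defects.

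**What to change.** 1. Keep the Day 1-92 tables as the all-cause summaries.
2. Add one table for onset from Day 93: treatment-related AEs and SAEs, and AESIs, by regimen. State that restriction in the title, and show duration of follow-up beside it; SAP 3.5.2 already derives this.
3. Replace the two open-ended tables with that table, or keep them with a footnote saying that collection is all-cause to the Week 12/Month 3 visit and limited to AESIs and related events afterwards.
4. In 2.1.1, replace the equation of 12 weeks with 92 days by a statement that Day 92 is Week 12 plus the 7-day visit window.
5. In 3.8.1.1, start the post-Betalutin period at Day 93, as in 3.5.2 and 3.8.1.3.

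The cost is one extra table, a date filter in existing programs and a few lines of SAP text. A few events move between tables. No new data are needed.

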Initial pharmacokinetics data were collected in Part A in a broad population of iNHL. Collection of further pharmacokinetics data was included in Part B to better characterise the pharmacokinetics of Betalutin and total lilotomab antibodies. Pharmacokinetic sampling in Part B is to be performed at selected centres and only for patients consenting for pharmacokinetic sample collection. Pharmacokinetic sample collection is not feasible at all sites participating in study 37-01 and ability to perform adequate sample collection is currently further limited due to restrictions related to COVID-19.

As of January 2021, no Part B patient has consented to pharmacokinetic sample collection, which may have been partly due to patients' reluctance to attend additional hospital visits during the COVID-19 pandemic.

Part C is added to specifically assess the pharmacokinetics of Betalutin and total lilotomab antibodies and is to be conducted at selected centres able and willing to perform adequate pharmacokinetic sample collection. In order to recruit enough patients in Part C, the population has been aligned with the population of Part A population, which is broader than Part B population and should allow for a sufficient amount of patients to be included at each participating site. Preliminary results from Part A have shown responses to study treatment in all populations of iNHL included in Part A (53), which allows their further inclusion in Part C.

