14.1.2.3 Part B – Population treated with “40/15” Regimen

Note - At the interim analysis, the SRC decided to discontinue the “100/20” treatment regimen, and continue with further recruitment in the “40/15” treatment regimen only.

A total of 87 patients, including the those from the interim analysis, will be recruited and treated with the “40/15” regimen.

With 87 patients, there will be more than 90% power to detect a difference of 18% in response rates using a two-sided exact test with a target significance level of 0.05, assuming the response rate under the null hypothesis is 30% and the response rate under the alternative hypothesis is 48%. If there are at least 36 responders in 87 patients, then there will be at least 97.5% chance that the true response rate will be at least 30%.

Moreover, with 87 patients, there will also be more than 90% power to detect a difference in complete response rate of 8% under the null hypothesis versus 20% under the alternative hypothesis.

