CRR	Complete Response Rate
CSR	Clinical Study Report
CT	Computed Tomography
CTCAE	Common Terminology Criteria for Adverse Events
DoCR	Duration of Complete Response
DoR	Duration of Response
ECG	Electrocardiography
ECOG	Eastern Cooperative Oncology Group
eCRF	Electronic Case Report Form
EU	European Union
FACT-Lym	Functional Assessment of Cancer Therapy–Lymphoma
FL	Follicular Lymphoma
γ GT	Gamma Glutamyl Transferase

HAMA	Human Anti-Murine Antibody / Human Anti-Mouse Antibody
HLA	Human leucocyte antigen
IRC	Independent Review Committee
ITT	Intent-To-Treat
LDH	Lactate Dehydrogenase
MBq	Mega Becquerel
MedDRA	Medical Dictionary for Regulatory Authorities
N/A	Not Applicable
NAb	Neutralising Antibody
NE	Not Evaluable
iNHL	indolent Non-Hodgkin Lymphoma
ORR	Overall Response Rate
OS	Overall Survival
PD	Progressive Disease
PFS	Progression-free Survival
PET	Positron-emission Tomography
PK	Pharmacokinetic
PR	Partial Remission
PT	Preferred Term
QoL	Quality of Life
RoW	Rest of World
SAE	Serious Adverse Event
SAF	Safety Analysis Set
SAP	Statistical Analysis Plan
SCT	Stem Cell Transplant
SD	Stable Disease
SI	International System of Units

SOC	System Organ Class
SPECT	Single Photon Emission Computed Tomography
SRC	Safety Review Committee
TEAE	Treatment Emergent Adverse Event
TFLs	Tables, Figures and Listings
WHO	World Health Organization

1 Introduction

This abbreviated statistical analysis plan (SAP) details the proposed analyses to be conducted by Veristat for the LYMRIT-37-01 phase I/II study (Part B) and the phase IIa expansion part (Part C).

Part A, dedicated to assessing the safety of various doses/regimens, was analysed under a separate SAP, Veristat study no: NOR18001.

In July 2022, LYMRIT-37-01 Part B and Part C were both terminated following slow recruitment. An ad hoc efficacy review of 61 patients (July 2022) who had received a dose of “40/15” and also had an Independent Review Committee (IRC) evaluated baseline and 3 month scan and efficacy assessment was conducted. Following this, the decision was taken to terminate the study. Details of this interim analysis are documented separately.

This analysis will be restricted to:

To support the final (close out) CSR, the efficacy and safety will be evaluated at a minimum of 3 months follow-up after the final patient has received the “40/15” regimen in Part B.

Specifically, this means that the following data will be formally analysed:

Table 1: Data to be reported: Analysis datasets and TFL’s to be produced

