3.1 General

Summary statistics for continuous variables will consist of number of non-missing observations (n), mean, standard deviation, minimum, 25th percentile, median, 75th percentile and maximum, unless specified otherwise. The precision (number of decimal places) of these variables is defined in the tables, figures and listings (TFLs) shells document – minimum and maximum will be presented to the same level of precision as the raw data; mean, median, percentiles will be presented to 1 additional decimal place; standard deviation will be presented to 2 additional decimal places.

For categorical variables the number and percentage of participants in each category will be presented, based on the number of non-missing observations apart from disposition of participants, protocol deviations, background and demographic characteristics, prior and concomitant medications/procedures and adverse events where the percentage will be based on the number of participants in the analysis set.

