3.4 Data Presentation

The TFLs will present the dose regimens (where relevant) as detailed below:

Table 4: LYMRIT-37-01 study, Part B/C Treatment Group Descriptors

Order	Descriptor for Dose Regime (where relevant) to be presented in TFLs	Meaning of Descriptor
1 [1]	40 / 12.5	40 mg lilotomab plus 12.5 MBq/kg Betalutin
2	40 / 15	40 mg lilotomab plus 15 MBq/kg Betalutin
3	100 / 20	100 mg/m ² lilotomab plus 20 MBq/kg Betalutin
4 [1]	Received Rituximab only	Received Rituximab only
5 [1]	Enrolled no treatment	Enrolled but did not receive any trial treatment
6 [1]	Screen failure	Participants in the screened set who failed screening (i.e. are not eligible to join the study per the eligibility eCRF page).

[1] In table summaries, if there is insufficient space to present all treatment groups on a single page, these dose regimens will be presented on the next page.

The data will be summarised in tabular form by Study Part (i.e. B / C) and dose regimen.

Results from scheduled visits will be tabulated. Unscheduled visits will be included in assessments of maximum post-baseline. All assessments will be listed.

Table 5: Populations to be used for output

Type of data	Listings	Summaries
Disposition	Screened set	Screened set
Demographic characteristics and baseline	SAF	SAF, Efficacy Analysis Set
Efficacy	SAF	Efficacy Analysis set

AE's and lab data	SAF	SAF
-------------------	-----	-----

Listings will be sorted by Study Part (i.e. B / C) and dose regimen, patient number and date/time of assessment.

Graphical presentations of the data will also be provided where appropriate.

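### Open-ended TEAE percentages by regimen ignore unequal follow-up, so at equal late risk 40/15 shows fewer post-Day-92 events than 100/20

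*SAP*

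**What the plan says.** SAP 3.8.1.3 asks for "the number of events and the number and percentage of participants experiencing TEAEs by SOC and PT", over two onset windows. One runs from Day 1 to Day 92. The other is "TEAE onset from Day 1 onwards", with no upper limit. In Table 6 all six summaries use the Day 1–92 window, and two of them (TEAEs by SOC and PT, and serious TEAEs) also use the open-ended one.

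SAP 3.1 fixes the denominator by listing "adverse events where the percentage will be based on the number of participants in the analysis set". Table 5 makes that set the Safety Analysis Set.

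On columns, SAP 3.4 states: "The data will be summarised in tabular form by Study Part (i.e. B / C) and dose regimen". SAP 3.8.1.2 exempts only the baseline-period table from the regimen split. SAP 3.8.1.3 itself mentions only an overall summary, so regimen columns in the open-ended tables are an inference, though a strong one.

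On timing, SAP 1 says efficacy and safety will be "evaluated at a minimum of 3 months follow-up after the final patient has received" 40/15 in Part B. Protocol 14.1.2.3 records: "At the interim analysis, the SRC decided to discontinue the" 100/20 regimen, with later recruitment to 40/15 only.

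On follow-up, SAP 3.5.2 says: "Descriptive statistics for the duration of follow-up (months) will also be included where". It then defines duration by the latest date known alive. This goes into the disposition summary and is not linked to any adverse event percentage.

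**The concern.** A crude percentage counts patients with an event during whatever time they were watched. It can be compared between columns only if the columns were watched for similar lengths of time. Here they were not. All 100/20 patients are early patients, whereas the 40/15 column mixes patients randomised alongside them with later recruits.

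The affected part is narrow but important. Protocol 13.2 limits reporting after 12 weeks to new AESIs and treatment-related AEs and SAEs. Protocol 13.1.7 names the long-term worry: secondary malignancy, myelodysplastic syndrome, acute leukaemia and aplastic anaemia. The two open-ended tables are the only adverse event summary tables in the SAP that can contain such late events. The related, serious related, CTCAE-grade and most-frequent tables all stop at Day 92. AESIs otherwise appear only as a raw dataset (SAP Table 2) and as a listing flag.

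Protocol 5.3.2 lists comparison of the two regimens, safety included, as a secondary objective. A reader of the close-out report could therefore see the selected regimen with fewer late harms purely because it was observed for less time.

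**Working it through.** The documents give no adverse event rate, person-time or follow-up figure by regimen, so there is no plan figure to reproduce. The check asks what the columns would show if the late risk were identical.

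**Inputs from the documents**
- The interim covered 47 patients (Protocol 4.8.10), randomised 1:1 (Protocol 6.1). I take 24 on 40/15 and 23 on 100/20.
- 61 patients had received 40/15 and had IRC baseline and 3-month scans in July 2022 (SAP 1). This is a stand-in for the number dosed, which is not given. The plan was 87 (Protocol 14.1.2.3).
- Randomisation had stopped before Version 15, whose section 4.8.6 is dated by "As of January 2021, no Part B patient has consented to pharmacokinetic sample collection". From January 2021 to the July 2022 termination (SAP 1) is 18 months. Each 100/20 patient thus had at least about 18 months of potential follow-up, or about 15 months after Day 92.

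**Assumed, not in the documents**
- Data cut in July 2022.
- The other 61 − 24 = 37 patients on 40/15 dosed evenly from January 2021 to April 2022, giving 0 to 15 months after Day 92 (mean 7.5).
- Constant late hazard *h*, the same in both regimens.
- No deaths or withdrawals.

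**Step 1: mean late time at risk.** Let *L* be the late time of a randomised patient. For 40/15 the mean is (24 × *L* + 37 × 7.5)/61.
- *L* = 15 months: (360 + 277.5)/61 = 10.45 months; ratio to 100/20 = 10.45/15 = 0.70.
- *L* = 27 months (30 months of follow-up in all): (648 + 277.5)/61 = 15.17 months; ratio 15.17/27 = 0.56.

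**Step 2: crude percentages.** For 100/20 this is 1 − exp(−*hL*). For the 37 later patients it is 1 − (1 − exp(−*hT*))/(*hT*) with *T* = 1.25 years. At *h* = 0.10 per year the later patients show 6.0%.
- *L* = 15 months: 100/20 shows 11.8%; 40/15 shows (24 × 11.75 + 37 × 6.00)/61 = 8.3%; ratio 0.70.
- *L* = 27 months: 100/20 shows 20.1%; 40/15 shows (24 × 20.15 + 37 × 6.00)/61 = 11.6%; ratio 0.57.

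For *h* from 0.05 to 0.20 the ratios are 0.70–0.71 and 0.57–0.59.

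**Step 3: vary the undocumented inputs.**
- Cut six months later, adding 6 months to everyone: (24 × 21 + 37 × 13.5)/61 = 16.45 months, ratio 0.78; or (24 × 33 + 37 × 13.5)/61 = 21.17 months, ratio 0.64.
- Later patients dosed from July 2020 (mean late time 10.5 months), *L* = 27: (648 + 388.5)/61 = 16.99 months, ratio 0.63.
- A different accrual model: randomised patients dosed over 1.5 years ending 3 months before the interim; 40/15 recruited evenly for 1 to 3 more years; cut 3 months after the last dose; *h* from 0.03 to 0.20. The ratio is 0.55–0.67 with 61 patients on 40/15 and 0.46–0.60 with 87. With 61 patients, 2 more years and *h* = 0.05, the columns read 13.9% and 8.4%, on mean late follow-up of 3.00 and 1.79 years.

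Every case is below 1, and together they span roughly 0.5 to 0.8.

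**Step 4: size in patients.** Among 23 on 100/20, the gap of 11.8% against 8.3% is 0.8 of a patient, and 20.1% against 11.6% is about 2. For scale, 3 of 23 (13.0%) has an exact 95% CI of 2.8% to 33.6%.

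**Step 5: effect of a person-time denominator.** Under the same assumptions, expected events divided by patient-years at risk equal *h* in both regimens, so the artefact disappears.

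**The case against.** The best defence is that the SAP makes no such comparison. Its safety objective (2.2) is to characterise the safety profile, with no regimen contrast. It plans no adverse event test or between-regimen difference, and section 3.10 declares large changes from the protocol. All six Table 6 summaries exist for a common Day 1–92 window. Follow-up duration is summarised. The listings give onset times, a post-treatment flag and an AESI flag, and deaths are listed with dates. Late events will be few. The regimen was chosen at the interim and the study has since been terminated.

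Most of this stands, and it limits the point. Early events are compared fairly, no formal test is biased, and a careful reader could spot the imbalance. It does not remove the point. The Day 1–92 tables cannot show late harms. The follow-up statistics sit in a different table. Side-by-side columns invite the comparison that Protocol 5.3.2 names.

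It is also fair that death or withdrawal would shorten the longer window most and shrink the gap. A person-time rate is imperfect too: it assumes a roughly constant hazard, and it cannot make later 40/15 patients concurrent with the randomised 100/20 patients.

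A reader might infer that the choice of 40/15 rested on this artefact. The documents do not support that. The choice was made at the interim, on the totality of safety and efficacy data from patients with at least 3 months of observation, before these tables were specified.

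**Conclusion.** The point holds for the post-Day-92 part of the two open-ended tables. At equal late risk and similar drop-out, the crude percentages show fewer late events on 40/15 than on 100/20. That direction follows from when the regimens recruited. It also rests on reading SAP 3.4 as giving these tables regimen columns.

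A reader might infer from the worked examples that a definite share of late 40/15 events, say 30% to 44%, will be missed. The documents do not support a figure. Cut-off date, accrual dates, numbers dosed, drop-out and the late hazard are all absent. The ratio of roughly 0.5 to 0.8 is an illustration of scale, and in the worked examples it amounts to about one or two patients. The share of all TEAEs that start after Day 92 is also unknown, so no distortion of a whole table can be stated.

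The change is still worth making: it is cheap, and these are the only summary tables in which late harms appear.

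**What to change.** In SAP 3.8.1.3 and Table 6:

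1. State that any side-by-side regimen comparison uses the Day 1–92 tables.
2. Keep the two open-ended tables as descriptive. Show median follow-up in each regimen column and add a note that percentages including post-Day-92 events are not comparable between regimens.
3. Add one summary of post-Day-92 events per regimen, in three rows: any TEAE, serious TEAE, and AESI or secondary malignancy. Give patients with an event and patient-years from Day 93 to the first event, death, withdrawal or end of adverse event observation, with an exact Poisson 95% CI. Alternatively, give cumulative incidence at common times with death as a competing event.

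The latest date known alive in SAP 3.5.2 should not by itself close the person-time. It draws on survival follow-up and can run past the end of adverse event observation. Three rows also avoid a separate denominator for every SOC and PT line.

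The cost is SAP wording, one extra table and one derived end date, from onset and follow-up dates already collected. The downsides are few late events with wide intervals, a rate that assumes a roughly constant hazard, and a comparison that remains non-concurrent for the later 40/15 patients.
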